Despite these encouraging findings on the beneficial effects of resistance-based exercise on sarcopenia and CAD separately, no study has been done to examine its effects on patients having the co-existence of sarcopenia and CAD, leaving a significant gap in the literature. Indeed, enabling this vulnerable cohort to adopt and maintain regular resistance exercise remains a great challenge. Older adults have reported perceived difficulty, time constraints and boredom as obstacles to resistance exercise.¹⁸ An effective yet sustainable intervention needs to address these challenges/obstacles. Previous studies have highlighted the importance of enhancing older people's self-efficacy in performing exercise in order to improve exercise adoption and adherence.^{19,20} Moreover, opportunities to resistance training, indeed, emerge around the clock in the routine of an individual. Assisting older adults to integrate exercise into daily activities can maximize the training benefits and overcome barriers to exercise, and thus improve exercise adoption and adherence.²¹ Therefore, this study aims to develop a strength-building lifestyle-integrated intervention for sarcopenic CAD patients and to examine the feasibility and preliminary effects of this intervention on skeletal muscle mass, muscle strength, physical performance, cardiac-related functional status and health-related quality of life (HRQoL), psychological distress, major adverse cardiovascular and cerebral events (MACCE) and hospital readmission rates. Physical performance will be the primary outcome, while the remaining will be the secondary outcomes.

Research plan and methodology

Study design

This study will include an assessor-blinded two-arm prospective pilot randomized controlled trial (RCT) and a qualitative study to determine the feasibility, acceptance and engagement experience of the participants in the strength-building lifestyle-integrated intervention with assessments measured at baseline, 3 months and 6 months after randomization.

Study setting and participants

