This study will recruit subjects in Care for Your Heart, a cardiac patient mutual support organization. Patients fulfilling the following eligibility criteria will be invited to join the study: 1) Chinese adults with a confirmed diagnosis of CAD; 2) age ≥ 60 years or older; 3) presence of sarcopenia according to the diagnostic criteria defined by the Asian Working Group for Sarcopenia²²: low skeletal muscle mass (measuring the appendicular skeletal muscle mass with bioelectrical impedance analysis: <7.0 kg/m² for men and <5.7 kg/m² for women), accompanied by low muscle strength (handgrip strength <28 kg for men and <18 kg for women); 4) free from ischemic symptoms when performing activities of daily living; 5) living in the community. Patients who cannot read Chinese or with impaired cognition (Abbreviated Mental Test score ≤ 6) or communication, a pacemaker or implantable cardioverter defibrillator precluding the use of bioelectrical impedance analysis for body composition assessment, physical limitations precluding exercise training, with any contraindication for exercise, any terminal or unstable conditions (e.g., malignant arrhythmia, severe aortic stenosis, cancer), admitted or recently completed a structured cardiac rehabilitation program within the past 6 months will be excluded.

The sample size for this pilot study was estimated based on the primary outcome (i.e., functional capacity) to be measured by the Short Physical Performance Battery (SPPB). The literature indicated the minimal clinically importance difference is >1 point of SPPB²³ and the SD estimate is 4.2 in the population with cardiovascular disease, giving rise to the standardized effect size as 0.28. According to the method proposed by Whitehead et al.,²⁴ a sample size of 20 per study arm for the pilot study would give the future main trial 80% power at 5% level of significance to detect the between-group changes in the primary outcome at post-intervention time points. The total sample size is therefore 40. They will be randomly allocated in a 1:1 ratio, to receive the strength-building intervention or usual care. All participants in the intervention group will be invited to take part in a face-to-face qualitative interview to explore the feasibility and acceptability of the intervention. The interviews will be conducted individually in the center of the Care For Your Heart. Each interview will be audio-recorded and will last for approximately 60 minutes.

Control group: Usual care

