Various methods will be used to monitor and optimize the fidelity of the study intervention. Assessments and record forms will be use to document the exercise prescription and progression. Participants’ attendance, exercise dose, performance and training response will be documented. A standardized manual will be developed to guide the delivery of each education session. The manual will also delineate the principles of exercise prescription and progression. Moreover, the 30% of the intervention sessions will be randomly selected

for fidelity monitoring by the principal investigator. Face-to-face sessions, in-person and remotely supervised sessions will be videotaped with participants' consent. Two post-doctoral fellows, who will be independent of the team will review the recorded videos and complete a performance checklist. The collected data will be used to evaluate the feasibility of the intervention.

Outcome evaluation

The following measuring tools/methods will be used for outcome evaluation at baseline (T0), immediate post-intervention (T1), and 3 months post-intervention (T2). Physical performance will be the primary outcome, while the rest will be the secondary outcomes.

Physical performance: The Short Physical Performance Battery³¹ will be used to assess physical performance and is well validated and widely adopted in clinical and research settings. It is a brief performance-based assessment consisting of 3 timed-tasks, including standing balance, walking speed, and chair stand tests. The timed results will be rescaled to obtain a score ranging from 0 to 12, higher scores indicate better physical performance.

Muscle mass and strength: The appendicular skeletal muscle mass (ASM) will be measured with the bioelectrical impedance analysis (In-Body). This is one of the gold-standard evaluation tools suggested by international guidelines for assessment of muscle mass. It is widely used in research and hospital setting for clients with sarcopenia. The muscle strength will be measured with a hydraulic dynamometer (Jamar). The standard protocol suggested by international guidelines will be followed, the maximum reading of at least 2 trials using the dominant hand in a maximum-effort isometric contraction will be recorded.

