Statistical analysis of the outcome comparisons will be performed on the basis of the intention-to-treat principle. Descriptive statistics will be used to describe the characteristics of the sample, the feasibility of, acceptance, and compliance with the intervention. The baseline characteristics will be compared between the study groups using a t-test, chi-square test or Fisher's exact test where appropriate. Repeated measure ANOVA will be used to determine the effects of the intervention by comparing differential between group changes across the 3 time-points. All statistical analyses will performed using IBM SPSS 27.0. All statistical tests will be two-sided, and a p-value of less than 0.05 will be considered statistical significant. Content analysis will be used to analyze the qualitative data. These data will be used to optimize the intervention design and feasibility for the full scale randomized controlled trial.

References:

2. World Health Organization. Cardiovascular diseases. 2021; [https://www.who.int/news-room/fact-sheets/detail/cardiovascular-diseases-\(cvds\)](https://www.who.int/news-room/fact-sheets/detail/cardiovascular-diseases-(cvds)), 2021.

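### The pilot's outcome analysis is a low-powered significance test, with no commitment to estimates and confidence intervals at T1 and T2 or to an SPPB SD

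*Combined protocol and SAP*

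**What the plan says.** - **Aim (end of the background).** The study will "examine the feasibility and preliminary effects of this intervention". Physical performance is the primary outcome.
- **Sample size (Study setting and participants).** Twenty per arm is justified by what it offers a later study: "future main trial 80% power at 5% level of significance to detect the between-group changes in the primary outcome at post-intervention time points". Its inputs are a minimal important difference of more than 1 SPPB point, taken from the literature, and an SD: "the SD estimate is 4.2 in the population with cardiovascular disease". No power or precision is given for the pilot itself.
- **Time points (Outcome evaluation).** Baseline (T0), "immediate post-intervention (T1), and 3 months post-intervention (T2").
- **Outcome analysis (Data analysis).** "Repeated measure ANOVA will be used to determine the effects of the intervention by comparing differential between group changes across the 3 time-points".
- **Threshold (Data analysis).** The rule for every test, two-sided throughout, is that "a p-value of less than 0.05 will be considered statistical significant".
- **Descriptive results (Data analysis).** "Descriptive statistics will be used to describe the characteristics of the sample, the feasibility of, acceptance, and compliance with the intervention". Outcome differences between the groups are not in this list.

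**The concern.** The sample size serves one purpose and the outcome analysis is worded for another. A pilot sized to inform a later trial would normally report how large the difference might be and how variable the outcome is. This plan describes a test meant to settle whether the intervention works, at the usual 5% level, and promises neither quantity.

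Two things are at stake. First, if the test has little power for the difference the protocol itself regards as important, a non-significant result says almost nothing, yet may be read as lack of effect. Second, an overall test across three time points yields one p-value. It does not show the size of the difference, or whether it is present at the end of the programme, three months later, or both. For an intervention whose last phase is habituation, persistence is a natural question.

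**Working it through.** **Inputs from the protocol.** 20 per arm, 1:1; difference 1 SPPB point (the protocol says more than 1, so this is the lower bound); SD 4.2; two-sided 0.05; three time points.

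**Assumptions not in the documents.** Within-person correlation ρ from 0 to 0.9, equal between all pairs of visits; complete data; a full 1-point difference at both T1 and T2; the ANOVA read as the overall group-by-time test.

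**1. The plan's own figures.** 2 × 20 = 40 agrees with the stated total. The rule that gives 20 per arm is cited but not reproduced in the documents, so it cannot be confirmed from them. The stated standardized effect of 0.28 does not follow from the stated inputs: 1/4.2 = 0.238. Both values are carried below.

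**2. Power of the group-by-time test.** The degrees of freedom are 2 and (40 − 2) × 2 = 76; the critical F is 3.117. The noncentrality is

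λ = (n/2) × Σ(dₜ − d̄)² / [SD² (1 − ρ)].

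For differences 0, 1, 1 the mean is 2/3, and the centred sum of squares is 4/9 + 1/9 + 1/9 = 2/3. With n = 20 and SD 4.2, λ = 10 × (2/3) / [17.64 (1 − ρ)] = 0.378/(1 − ρ). At ρ = 0.8 this is 1.89.

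| Setting | ρ = 0 | 0.5 | 0.7 | 0.8 | 0.9 |
|---|---|---|---|---|---|
| SD 4.2 (protocol) | 7.8% | 10.9% | 15.2% | 20.8% | 38.1% |
| Effect size 0.28 (protocol) | 9.0% | 13.3% | 19.5% | 27.5% | 50.6% |
| SD 3 (assumed) | 10.8% | 17.1% | 26.1% | 37.5% | 66.3% |
| SD 2 (assumed) | 18.8% | 34.1% | 53.2% | 71.8% | 95.7% |

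A simulation of 40,000 trials at SD 4.2 gave 7.8% at ρ = 0 and 20.4% at ρ = 0.8, in line with the formula.

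**3. Timing of the effect.** For a benefit lost by T2 (differences 0, 1, 0) the mean is 1/3 and the centred sum of squares is 1/9 + 4/9 + 1/9 = 2/3. This equals the value for a benefit kept at T2 (0, 1, 1). So λ and power are the same for both patterns at every ρ, and the overall test does not separate them.

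**4. What estimates would offer.** The 95% half-width for a between-group difference at one follow-up, at SD 4.2, with √(2/20) = √0.1:

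- Unadjusted: t(38) × 4.2 × √0.1 = 2.024 × 4.2 × 0.316 = 2.7 points.
- Change from baseline, multiplying by √[2(1 − ρ)]: 2.7, 2.1 and 1.7 points at ρ = 0.5, 0.7 and 0.8.
- Adjusted for baseline, t(37) × 4.2 × √(1 − ρ²) × √0.1: 2.3, 1.9 and 1.6 points at the same ρ.

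Baseline adjustment is the narrowest of the three at each of these correlations.

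**5. Precision of the SD.** An observed SD of 4.2 on 38 degrees of freedom has a 95% CI of 0.817 × 4.2 to 1.289 × 4.2, that is 3.4 to 5.4.

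**The case against.** **The threshold is only a convention.** A reader might infer that p below 0.05 is the pilot's sole criterion for an effect. The documents do not support that. The sentence sets alpha for all tests, including the baseline comparisons. It defines no success rule, and no decision to proceed is tied to it. This objection stands. What remains is that the section words the ANOVA as settling the effects and commits to no other outcome result.

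**Contrasts and estimates are not excluded.** This is also correct. The plan does not name the overall interaction test or rule out comparisons at T1 and T2. The power figures and the argument on timing therefore hold only if the overall test is the analysis.

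**Low power is normal in a pilot, and the inputs are uncertain.** Agreed. The sample size is not the fault, and no larger pilot is asked for. The documents give no correlation, and an SD of 4.2 is large for a 0-12 score. With a smaller SD and a high correlation, the test would detect 1 point more often than not.

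**Two further inferences go too far.** One is that the main trial must take its effect range from the pilot. The protocol takes its target difference from a published minimal important difference, so the SD is the main quantity the pilot can supply. The other is that significant results would exaggerate the effect. That bias requires estimates to be reported or used only when significant, and the documents state no such filter.

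**Conclusion.** The point holds as a cheap improvement, not as an error that invalidates the pilot. The outcome analysis is worded as a test of efficacy in a trial that was not sized for one, and the plan does not commit to the results that a study of preliminary effects can usefully give.

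On the protocol's SD and the assumptions listed, the overall test would miss a 1-point difference about 79-92% of the time at correlations 0-0.8, and about 62% of the time at 0.9. Dropout would lower the power, since 20 analysed per arm is the best case. The missing commitment to T1 and T2 estimates and to an SPPB SD does not depend on any assumed correlation or SD.

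**What to change.** In the Data analysis section, replace the statement that the ANOVA will determine the intervention's effects with one saying that the analysis will estimate its preliminary effects, and add:

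*Between-group differences at T1 and at T2, adjusted for the baseline value, will be reported as estimates with 95% CIs; p-values are exploratory and no efficacy conclusion will be drawn from them. The pooled within-group SPPB SD at each time point and the correlation with baseline will be reported, with a 95% CI for the SD, to inform the main trial.*

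**Cost.** Wording only: no new patients, visits or data. The sponsor gives up the option of claiming a significant effect from the pilot and must show the wide intervals calculated above.
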